3.10 Planned health technologies

Technology 1: Motivational interviewing

The main objective of MI will be to bring about changes in behaviour by enhancing motivation. Patients allocated to the MI group will receive 4 individual sessions lasting one hourevery fortnight for 2 months. A computerised assessment will be carried out using the Accu-Chek interview ⁶⁰ developed for use by patients with diabetes. This tool incorporates key MI tasks; a menu of self care behaviour change options; assessment of importance and confidence of change in a self care topic selected by the patient; and the identification of specific patient barriers that influence patient confidence around behaviour change. Work in the US and our pilot suggests it has face validity for patients ⁶¹. The advantages of a computerised assessment tool is that it increases motivation, self-efficacy and behaviour change. ⁶²At the first session the computer assessment will be conducted. The patient will select one self care topic from 7 options: self-monitoring of blood glucose, food and eating, exercise, hypoglycaemia, smoking, a topic provided by the patient and a "no topic today" option. The software generates a 1-page report for the patient that summarise the self-care topic identified by the patient. It also gives ratings of importance and confidence regarding

behavioural change and barriers to change in the topic identified by the patient. Following the Accu-Chek the patient and nurse will discuss the topic selected, exploring importance of change and building confidence regarding change.

Motivational interviewing techniques include non-challenging, non-judgmental and reflective communication, clarifying problems and advantages, information gathering and presenting options. Potential solutions to each barrier identified by the patient will be discussed as well as potential benefits from improvement in self-care. The discussion is then summarised and a specific action plan negotiated. The next three sessions will review the discussion and action plans from the previous session and then cover the topic selected on the day for discussion by the patient.

Technology 2: Motivational Interviewing plus Cognitive Behavioural Therapy

Participants will receive 4 sessions of MI as described above followed by 8 sessions of CBT. The main objective of CBT will be to enable the patient to identify and modify unhelpful diabetes specific cognitions and behaviours which may be contributing to poor glycaemic control. Eight individual sessions lasting one hour each over a 4-month period will be given. Treatment will be individualised, conducted collaboratively and follow a modified version of Kanfer and Schefft⁶³ seven phases of treatment: Phase 1 – assessment (behavioural analysis, life history, role of significant others, perception of diabetes); Phase 2 - establishing a therapeutic alliance; Phase 3 – generating the willingness to change; Phase 4 - giving the patient a rationale for treatment; Phase 5 - conducting the treatment; Phase 6 - monitoring and evaluating progress; Phase 7 - generalising the progress and ending treatment.

Each treatment session is structured. At the start of every session an agenda is agreed, which is patient led and guided by the therapist. This is to ensure that all issues are addressed within the time available. Sessions usually last up to one hour. Homework which takes the form of specific behavioural and cognitive goals which have previously been agreed are discussed. Success with homework and problems are discussed. New homework is negotiated and agreed. At the end of each session key points discussed are summarised. The nurse therapist always keeps in mind the end of treatment targets which have previously been agreed as these are to be worked towards systematically.

Techniques used will be tailored to the individual needs of the patient. A rationale will be given for those cognitive and behavioural changes which the patient and therapist has agreed upon. Interventions will include: involving significant others; normalising dietary, exercise and life style related behaviours; anxiety, worry and stress management; challenging negative automatic thoughts (anxiety or depression related); improving impulse control; behavioural experiments; activity scheduling; strategies for eliciting social support; assertiveness training.

Control group

Patients randomised to the control group, and the groups receiving MI and MI plus CBT, will have their usual diabetes care. The participating centres have agreed to a protocol of minimum acceptable diabetes care which is an annual review modelled on the protocol recommended by the Diabetes National Service Framework. All centres agree to the same aims of diabetes treatment of a HbA1c $\leq 7.0\%$ with no problematic hypoglycaemia (see Protocol for usual care: version 1 18.08.03)

3.11 Delivery of technologies It is important that both technologies are clearly defined and described to enable subsequent replication and use by other health professionals. Both technologies will be delivered by diabetes specialist nurses (DSN) and this will be achieved by several means:

1. The psychologist will pilot MI and CBT with supervision from TC, US, JT and KI. A protocol for supervision will be agreed upon.

2. A training manual will be written by the psychologist to ensure standardised training of diabetes nurse specialists in both MI and CBT. We will integrate training manuals for MI with in house and internet based training manual in MI.⁶⁴

3. A measure for assessing a set of competencies and skills will be used during training and throughout the trial. 65

4. Patients who will receive MI and/or CBT for the purposes of training the nurses only will be given a separate patient information sheet explaining the technologies and that the nurses are in training and their written consent will be required before they start (see patient information sheet and consent form for training version 1).

5 A treatment manual for use by the DSN will be written for both MI and CBT by the psychologist under the guidance of TC and UC. The manual will include a section on diabetes management as suggested by the patients in the focus group.

6. Audio-taping of all treatment sessions will be carried out and a random sample will be rated by the supervisor and an independent assessor blind to allocation.

7. The psychologist will give weekly group and individual supervision to the DSNs.

8. Patients in the MI group will receive their Accu-check print out of the problems they have identified. Patients in the CBT group will receive a series of information sheets, given at the end of each session, titled 'Living with Diabetes'. These will cover the CBT model and common problems encountered by people with diabetes.

9. The investigators will meet with the research team regularly to ensure the trial is running according to plan.

3.12 Outcome

Main outcome: this will be the glycaemic control, measured by HbA_{1c} at 12 months follow up. However, we will also check patients HbA_{1c} at 3, 6 and 9 months to measure whether improvement is stepwise, gradual or sustained.

Subsidiary outcomes at 12 months follow up to measure change:

1. Biological: diabetes complications status will be repeated if not done 3 months before or after end of 12 month follow up at annual diabetes review. Body mass index and blood pressure will be measured.

2. Diabetes specific cognitions: The Diabetes Specific Health Beliefs-Experience of Treatment and Benefit Barriers; Fear of Hypoglycaemia questionnaire; and Beliefs about Medicine Questionnaire.

3. Diabetes specific behaviour: The Summary of Diabetes Self – Care Activities..

4. Psychiatric morbidity: *Primary Care Evaluation of Mental Disorders (PRIME-MD PHQ);* *GHQ-12*; the Alcohol Use Disorders Identification Test and the Life Events questionnaire.

5. Quality of life: The Short Form-36; the EuroQOL; and the DQOL.

6. Costs: Client Services Receipt Inventory

7. Social support: from family, friends and health professionals will be examined by the *Significant Others Scale*.

8. Adverse events checklist. A list of adverse events if and when they are reported will be compiled. Potential adverse events presently identified include any death, psychiatric admission, medical admission, onset of complication secondary to rapid glycaemic control (painful neuropathy, accelerated retinopathy, hypoglycaemic episodes).

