3.8 Baseline measures

Socio-demographic: data will be collected on age, sex, level of education, occupation, marital status, self report ethnicity.

Biological: HbA_{1c} (measured at screening); duration of diabetes; complications - retinopathy will be measured by retinal photography;⁵² neuropathy will be measured using the vibration-perception threshold⁵³ and nephropathy will be measured using an early morning urine sample for albumin-creatinine ratio.⁵⁴ Body mass index and blood pressure will be measured.

Diabetes specific cognitions: The *Diabetes Specific Health Beliefs-Experience of Treatment and Benefit Barriers* subscale for insulin treated diabetes will be used to measure the patient's perspective of adherence to the diabetes regimen.⁵⁵ *Fear of Hypoglycaemia* questionnaire⁴⁶ will be used as worries are not adequately measured by the *Diabetes Specific Health Beliefs*. The Beliefs about Medicine Questionnaire will be used to elicit beliefs about the use of insulin.⁶⁷

Diabetes specific behaviour: The *Summary of Diabetes Self –Care Activities* questionnaire measures frequency of adherence to eating habits, exercise levels, glucose monitoring and medication.⁵⁶

Psychiatric morbidity: This will be measured using the *Primary Care Evaluation of Mental Disorders (PRIME-MD PHQ)*⁵⁷ which is a self report measure for depressive, anxiety, alcohol, somatoform and eating disorders and using the *General Health Questionnaire-12*.⁶⁸ The *Life Events Questionnaire*⁶⁹ will be used to determine perceived stress and the World Health Organisation's *Alcohol Use Disorders Identification Test* to measure alcohol consumption.⁷⁰

Quality of life: The *Short Form-36* ⁵⁸ will be used which has been used extensively in diabetes. The *EuroQOL*⁷¹ will be used in order to conduct a cost-utility analysis, and the *Diabetes Quality of Life* measure to look at diabetes-specific themes. ⁷²

Costs: *Client Services Receipt Inventory*⁵⁹ gives a detailed description of service use patterns, medication (including insulin), employment and household family responsibilities in the previous 3 months.

Social support: from family, friends and health professionals will be examined by the *Significant* Others Scale.⁶⁶

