3.13 Measures of process

At three monthly intervals insulin regime will be recorded in order to measure the total dose of insulin.

At 6 months from baseline, social support will be measured with the *Significant Other Scale* ⁶⁶ to assess how it mediates the effect of health technologies on glycaemic control.

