3.16 Statistical analysis

Data will be entered using SPSS and analysed using STATA. The success of randomisation will be assessed by comparing baseline characteristics. The difference in mean reduction of HbA_{1c} between the CBT, MI and control groups will be estimated using a linear mixed model incorporating fixed effects of group, time and group by time and a random effect for subjects. All available data will contribute to the analysis including data on subjects who dropped out or withdrew from the trial (intention to treat analysis). The same analysis will be used to identify other predictors, such as presence of diabetes complications and psychiatric morbidity and effect modifiers such as social support. Secondary outcomes (illness perceptions and diabetes specific behaviours) will be analysed using linear mixed models and generalised linear mixed models for dichotomous outcomes. We will model the change in mean HbA1c over time using a linear trend and a quadratic one if needed. The change over time is reflected by the linear trend, "the effect of time", and a treatment effect would correspond to a group by time interaction. A comparison of participants and non-participants of the RCT will be performed on socio-demographic data available from the databases. A comparison of the baseline characteristics of completers and non completers will be done. Economic analysis: Total average costs will be linked with the main outcome (improvement in HbA_{1c}) for each group in the form of a cost-effectiveness analysis. A cost-utility analysis will be conducted on the SF-36. This will offer a simpler decision rule and allow explorations of cost per quality-adjusted life-year (QALY) gained.

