6.3 Research coordinator

A research worker with training in epidemiology will be required to co-ordinate the study. He/she will liase with diabetes consultants to identify and contact the patients, liaise with all members of the research team, data collection and entry, conduct blind assessment at baseline, 6 months and 12 months follow up. He/she will organise meetings with the TSC and DMEC. The co-ordinator will be expected to enrol for a PhD studentship at GKT School of Medicine.

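### Utility is scheduled only at baseline and 12 months, so the cost-per-QALY analysis must assume the path in between and is liable to error if change is not linear

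*Protocol*

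**What the plan says.** Protocol 3.8 lists the SF-36 and the EuroQOL among the baseline measures and says that the EuroQOL "will be used in order to conduct a cost-utility analysis". Both return in 3.12 ("Quality of life: The Short Form-36; the EuroQOL; and the DQOL"), under the heading "Subsidiary outcomes at 12 months follow up to measure change".

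Where the protocol wants values in between, it names them: HbA1c at 3, 6 and 9 months (3.12), the insulin regimen every three months (3.13), and one questionnaire at mid-year (3.13: "At 6 months from baseline, social support will be measured"). Section 6.3 has the research coordinator "conduct blind assessment at baseline, 6 months and 12 months follow up" but does not say what the 6-month assessment contains.

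Section 3.16 plans a cost-utility analysis that is to "allow explorations of cost per quality-adjusted life-year (QALY) gained". It gives no rule for the period between measurements.

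On treatment timing, 3.10 says that MI patients "receive 4 individual sessions lasting one hourevery fortnight for 2 months". For the combined arm, "Participants will receive 4 sessions of MI as described above followed by 8 sessions of CBT", and the CBT part runs over four months. Treatment therefore ends at about month 2 with MI and at about month 2 + 4 = 6 with MI plus CBT.

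Section 3.16 names the SF-36 for the cost-utility analysis, whereas 3.8 names the EuroQOL. That conflict needs its own correction. It does not alter this point, because both instruments have the same schedule.

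**The concern.** A QALY total over the trial year is the area under the utility curve. Two measurements give only its end points, and the natural interpolation is a straight line. An analysis plan can choose the interpolation rule, but it cannot recover utilities that were never collected. The schedule is therefore a matter for the protocol.

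The protocol gives no ground for assuming linear change in utility. Both active treatments stop by mid-year, and for HbA1c section 3.12 treats the shape of change as something to be found out. A benefit that comes early and lasts would be undercounted. A benefit that has gone by month 12 would not be counted at all. At stake is the cost per QALY of each technology against usual care and, less predictably, of one technology against the other.

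**Working it through.** The plan states no utility or QALY figure, so there is none to reproduce. The paths below are assumptions, chosen to show the range.

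**Inputs.** End of treatment T = 2 months (MI) and T = 6 months (MI plus CBT), from 3.10. Utility at 0 and 12 months, from 3.8 and 3.12. Let d be the peak utility gain over baseline, with usual care unchanged. Areas use the trapezium rule, in years.

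**Two-point estimate.** With a gain g at month 12, the QALY gain is (0 + g)/2 = 0.5g, whatever happened in between.

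**Assumed true paths.** Utility rises linearly to d at month T, then moves linearly to g at month 12. The true area is (T/12)(d/2) + ((12 − T)/12)(d + g)/2.

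- *Kept (g = d).* MI: 0.083d + 0.833d = 0.917d. MI plus CBT: 0.25d + 0.50d = 0.75d. Two points give 0.50d.
- *Half lost (g = 0.5d).* MI: 0.083d + 0.625d = 0.708d. MI plus CBT: 0.25d + 0.375d = 0.625d. Two points give 0.25d.
- *All lost (g = 0).* MI: 0.083d + 0.417d = 0.50d. MI plus CBT: 0.25d + 0.25d = 0.50d. Two points give 0.
- *Linear to month 12.* True area 0.50d; two points give 0.50d.

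**With month 6 added.** The estimate is 0.5 × (0 + u6)/2 + 0.5 × (u6 + g)/2. For MI, u6 is d, 0.8d and 0.6d on the three nonlinear paths, giving 0.75d, 0.525d and 0.30d. For MI plus CBT, u6 = d, and the estimate is exact on these paths.

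| Path | MI, 0/12 | MI, 0/6/12 | MI plus CBT, 0/12 | MI plus CBT, 0/6/12 |
|---|---|---|---|---|
| Kept | −0.417d | −0.167d | −0.250d | 0 |
| Half lost | −0.458d | −0.183d | −0.375d | 0 |
| All lost | −0.500d | −0.200d | −0.500d | 0 |
| Linear | 0 | 0 | 0 | 0 |

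On the nonlinear paths month 6 cuts the MI error by 60% (for example 0.417d to 0.167d) but does not remove it. Measuring at 3, 6, 9 and 12 months would leave 0.042d to 0.050d for MI.

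**A second model for the two active arms.** Both arms receive the same MI in months 0 to 2. Suppose MI has the same effect in both and CBT adds a gain e between months 2 and 6 that is kept. The true difference between the arms is (4/12)(e/2) + (6/12)e = 0.667e. Two points give 0.5e (error −0.167e). Three points give 0.5(e/2) + 0.5e = 0.75e (error +0.083e).

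**Scale.** If d were 0.05 (an assumption), the two-point errors of 0.25d to 0.50d would be 0.0125 to 0.025 QALY per patient.

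**The case against.** The strongest objection concerns the comparison of the two technologies. A reader might infer from the table that, when the gain is kept, MI has a true advantage of 0.917d − 0.75d = 0.167d which two-point measurement hides. The documents do not support this. It requires the MI arm to have gained d by month 2 while the combined arm, after the same MI, has gained only d/3. If the shared MI yields d by month 2 in both arms and the final gain is equal, the two paths coincide. The error is then 0.417d in each arm, and there is no advantage to lose. Equal final gains are also not what the trial hypothesises for glycaemic control (3.1, subsidiary hypothesis ii). This objection stands in full.

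Nor does month 6 reliably repair that comparison. On the tabled paths the between-arm discrepancy in error stays at 0.167d if the gain is kept, rises from 0.083d to 0.183d if half is lost, and rises from 0 to 0.200d if all is lost. On the shared-MI path it falls from 0.167e to 0.083e in size. This also stands: the effect on MI versus MI plus CBT depends on the path.

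The reach of the point is limited too. Objective 1.2 concerns cost effectiveness for glycaemic control, and 3.16 links costs to HbA1c, which is measured through the year. Cost per QALY is an additional exploration.

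Finally, the absence of a 6-month utility measure is a reading of 3.8, 3.12 and 3.13, because 6.3 leaves the content of that assessment open. It is the natural reading, since the protocol names its other intermediate measures. If a 6-month utility measure is intended, the schedule should say so.

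**Conclusion.** The point holds as a weakness in the measurement schedule of the cost-utility analysis. With utility at 0 and 12 months only, straight-line interpolation fixes the QALY gain at half the 12-month change. If the peak gain d is reached by the end of treatment, each active arm is understated against an unchanged usual-care arm by 0.25d to 0.50d on the paths tried. All of these paths are assumptions, since the documents give no utilities.

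A reader might go further and conclude that QALYs will certainly be wrong, and by different amounts in each arm. That does not follow. The error is zero if change is linear, and it is equal in the two active arms if the gain is fully lost by month 12. The supportable statement is that QALYs are liable to be misestimated, to a degree that can differ by arm. The HbA1c outcome and its cost-effectiveness analysis are untouched. This makes it an inexpensive improvement to an additional analysis.

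**What to change.** In 3.12 and 3.13, add the utility questionnaire to the existing 6-month assessment in all three arms. In 3.16, state that QALYs are calculated as the area under the curve through 0, 6 and 12 months. This reduces the error against usual care on every nonlinear path in the table. It should not be presented as a cure for the MI versus MI plus CBT comparison.

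As an option, also collect the questionnaire at the existing 3- and 9-month HbA1c contacts, which would remove most of the remaining MI error.

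The 6-month addition costs a few minutes per patient and one more form to enter. It needs no extra visit, because the assessment is already planned. The optional contacts would each add a further form.

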3.14 Ethical arrangements

Risks and anticipated benefits: CBT and MI are extremely safe interventions with negligible risks for the trial participant and for society. If either technology was effective, this could improve the care that patients with T1DM receive safely and with little extra cost to the NHS. Informing potential participants: psychological interventions are safe. Consent: All patients will be asked to give written informed consent. They will be given a brief summary of the current evidence for psychological interventions in diabetes and the rationale behind randomisation. All patients will be given a copy of their signed consent form and information sheet and one will be filed in the medical notes. Confidentiality: The database that contains the patients' names addresses and unique identifier will be accessed only by the research co-ordinator and the principal investigator. All other

data will be stored separately where patients will be identified by their unique identifier. Time period: retention of trial documentation is estimated at ten years.

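### Adverse events are compiled only as reported while the arms have 0, 4 and 12 therapy sessions, so counts of self-reported events are open to ascertainment bias

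*Protocol*

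**What the plan says.** Protocol section 3.12 places adverse events as item 8 under "Subsidiary outcomes at 12 months follow up to measure change". The item is titled as a checklist. Its text then reads "A list of adverse events if and when they are reported will be compiled", followed by "Potential adverse events presently identified include any death, psychiatric admission, medical admission, onset of complication secondary to rapid glycaemic control", with painful neuropathy, accelerated retinopathy and hypoglycaemic episodes given in brackets as the complications meant. No interval, standard question, recall period or assessor is stated.

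Section 3.10 sets the therapy contacts:
- MI: "Patients allocated to the MI group will receive 4 individual sessions", fortnightly over 2 months.
- MI plus CBT: "Participants will receive 4 sessions of MI as described above followed by 8 sessions of CBT", the CBT part running over 4 months.
- Control: "Patients randomised to the control group, and the groups receiving MI and MI plus CBT, will have their usual diabetes care", so no trial therapy sessions.

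Section 3.11 has diabetes specialist nurses deliver both therapies.

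Contacts or measures common to all arms are HbA1c at 3, 6, 9 and 12 months and repeat complications status around 12 months (3.12), a three-monthly record of insulin regimen (3.13), and blind assessment by the research co-ordinator at baseline, 6 and 12 months (6.3). The service-use inventory, repeated at 12 months, looks back 3 months (3.8, 3.12). None of these places mentions asking about adverse events.

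**The concern.** If events enter the list only when someone happens to report them, the number recorded depends on how often a participant has an occasion to report. Here that differs by randomised arm. So does the content of the contact: hypoglycaemia is one of the self-care topics on the MI menu (3.10), and fear of hypoglycaemic attacks is the worked example in the CBT rationale (2.8). Events raised in a session also reach the trial through a nurse who knows the allocation.

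A second, smaller point is that one category is defined by its cause: "onset of complication secondary to rapid glycaemic control". The sample size section (3.15) assumes 12-month means of 8% with therapy and 8.8% in controls, so a reporter who knows the arm could class the same hypoglycaemic episode as an event in one arm and not in another.

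At stake is the reading of any between-arm difference in self-reported events. An excess with therapy could be detection alone, and a true excess could be dismissed as detection. Because this is a rule for data collection, a later analysis cannot recover events that nobody asked about.

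**Working it through.** The protocol gives no adverse event figure to reproduce. The check is a count of contacts, then an illustration of what that count could do.

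**1. Contacts per arm.** Therapy sessions: 0, 4, and 4 + 8 = 12. Adding the four quarterly HbA1c checks gives 4, 8 and 16 scheduled trial contacts.

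**2. Contacts that can matter.** Only contacts after an event can bring it to light. Assumptions, none of them from the protocol: equal true risk in all arms; events spread evenly over 12 months; therapy starts at randomisation and is fully attended; MI sessions at 0.5, 1, 1.5 and 2 months and CBT sessions every half month from 2.5 to 6 months; the same chance p of a report at every contact.

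The mean number of contacts after an event is the sum of the contact times divided by 12:
- Usual care: (3 + 6 + 9 + 12)/12 = 2.5
- MI: 2.5 + (0.5 + 1 + 1.5 + 2)/12 = 2.92
- MI plus CBT: 2.5 + (0.5 + 1 + … + 6)/12 = 2.5 + 39/12 = 5.75

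**3. Capture probability.** For an event with k contacts still to come, capture = 1 − (1 − p)^k, averaged over the time of the event. The values of k are:
- Usual care: 4, 3, 2, 1 in successive quarters.
- MI: 8, 7, 6, 5 in the first four half months, 4 in month 3, then 3, 2, 1 in the remaining quarters.
- MI plus CBT: 16, 15, 14, 13, 12, 11, 9, 8, 7, 6, 5, 4 in the first twelve half months, then 2 and 1 in the last two quarters.

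Worked at p = 5%:
- Usual care: (0.1855 + 0.1426 + 0.0975 + 0.0500)/4 = 0.1189.
- MI plus CBT: mean 0.38925 over months 0–6 and (0.0975 + 0.0500)/2 = 0.07375 over months 6–12; overall (0.38925 + 0.07375)/2 = 0.2315.
- Ratio: 0.2315/0.1189 = 1.947.

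| p per contact | Usual care | MI | MI plus CBT | Ratio, MI | Ratio, MI plus CBT |
|---|---|---|---|---|---|
| 5% | 0.1189 | 0.1350 | 0.2315 | 1.136 | 1.947 |
| 10% | 0.2262 | 0.2510 | 0.3831 | 1.109 | 1.694 |
| 20% | 0.4096 | 0.4376 | 0.5638 | 1.068 | 1.377 |
| 50% | 0.7656 | 0.7736 | 0.8073 | 1.010 | 1.054 |

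**4. Where the difference lies.** After month 6 the remaining contacts (9 and 12 months) are the same in every arm, so the ratio there is 1. All of the excess comes from events in the first 6 months. At p = 5% the MI plus CBT ratio in that period is 0.38925/[(0.1855 + 0.1426)/2] = 2.37.

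**5. Sensitivity.** Later sessions raise the ratios, since each session adds its time divided by 12 to the mean contacts. Missed sessions lower them. A higher chance of mention in a one-hour session than at a blood test raises them.

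**6. Event types.** Death does not depend on a participant volunteering it. Complications status is measured again around 12 months in all arms. The 12-month inventory covers admissions in about months 9–12 only. That leaves hypoglycaemic episodes, painful symptoms and earlier admissions as the exposed group.

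**The case against.** The strongest reply is that the item is titled a checklist and sits under the 12-month outcomes, so it may be meant as an instrument put to everyone at 12 months, with interim reports added. That reading is possible, but the item's text does not say so. Even if right, it would leave interim reports unequal between arms.

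Usual-care participants are also not out of sight. They have quarterly HbA1c and insulin records, blind assessments at 6 and 12 months, repeat complications status and an agreed annual review. This stands, and it limits the bias. It does not remove it, because none of these contacts is tied to adverse event questions.

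Several stronger readings are tempting and should not be drawn:
- From the totals of 4, 8 and 16 contacts a reader might compute ratios of 3.0, 2.4 and 1.6 for MI plus CBT at 5%, 10% and 20%. That counts contacts held before the event occurred. Therapy is front-loaded, so these figures are too high.
- A reader might infer that the safety comparison is biased or uninterpretable as a whole. The size depends on reporting rates that the protocol does not give, it is near nil at 50% per contact, and some event types are barely exposed. Section 3.16 names no between-arm test of adverse events.
- A reader might set "CBT and MI are extremely safe interventions with negligible risks" in section 3.14 against the list in 3.12 as a contradiction. Judging a risk small while naming potential events to watch for is consistent.
- The causal wording affects one category only; deaths and admissions carry no attribution.

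**Conclusion.** The point holds in limited form. As written, item 8 does not secure equal ascertainment across arms with 0, 4 and 12 therapy sessions. Counts of self-reported events are open to bias that would make therapy look worse, mainly MI plus CBT and mainly for events in the first 6 months. For MI alone the effect is small under every rate tried (ratio at most 1.14). For MI plus CBT it runs from about 1.9 at 5% per contact to 1.05 at 50%. These ratios are illustrations under the assumptions above, not estimates for this trial. The documents support saying that such counts can be biased, not that they are. This is a worthwhile and cheap improvement rather than a flaw in the main outcome, which it does not touch.

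**What to change.** Amend section 3.12, item 8, so that the checklist is put as the same fixed questions in all three arms at the existing 3, 6, 9 and 12 month contacts. For each listed event, ask whether it occurred and how many times since the last common contact, without asking whether rapid glycaemic control caused it. At 6 and 12 months the blinded research co-ordinator, who already assesses then, should ask. Base any between-arm comparison on these answers alone, and list events volunteered in therapy sessions separately so that they remain visible for safety oversight.

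The cost is a short form and a few minutes at contacts that already take place. The remaining weakness is some recall error over 3 months, which would apply to all arms on the same schedule.
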